1.4.2 Statistical hypothesis, model, and method of analysis

The best overall response rate (CR/PR/SD/PD/UNK) was presented together with the appropriate two-sided confidence interval for the ITT set. Since the one-sided alpha was set to 10%, two-sided 80% confidence intervals were presented. Exact confidence intervals were computed according to the method of Clopper and Pearson.

The absolute number of patients showing a best overall response of CR, PR or SD was determined to conclude preliminary activity or non-activity of the study drugs in this patient population according to the rules outlined in CSP [section 10.2](#). Furthermore, the lower limit of the confidence interval was used to support the decision in favor of p_0 or p_1 : if the lower limit of the confidence interval overlapped p_0 , the hypothesis that p is greater than or equal to p_1 could be rejected; on the other side, if the lower limit of the confidence interval excluded p_0 , the hypothesis that p is greater than or equal to p_1 could be accepted.

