Arm II:	Patients with progressive GIST after failure or intolerance of treatment with imatinib or sunitinib in 1st and 2nd line
	Starting dose: RAD001 10 mg/day
	24 patients to be accrued in a single stage
Arm III:	Patients with progressive or metastatic alveolar soft part sarcoma (ASPS)
	Starting dose: RAD001 10 mg/day
	10 patients to be accrued in a single stage

Studies with other mTOR-inhibitors have shown a significant clinical benefit in patients with soft tissue sarcoma. Therefore, the 10mg daily dose of RAD001 has been selected as the treatment regimen for this study.

In cancer patients with hepatitis B, whether carriers or in chronic state, use of antivirals during anticancer therapy has been shown to reduce the risk of hepatitis B virus (HBV) reactivation and associated HBV morbidity and mortality (Loomba et al. 2008).

Screening for hepatitis B

Prior to starting study drug the following three categories of patients should be tested for hepatitis B viral load and serologic markers, that is, HBV-DNA, HBsAg, HBs Ab, and HBe Ab:

1. All patients who currently live in (or have lived in) Asia, Africa, Central and South America, Eastern Europe, Spain, Portugal, and Greece.
[<http://wwwnc.cdc.gov/travel/yellowbook/2010/chapter-2/hepatitis-b.aspx#849>]
2. Patients with any of the following risk factors:
 - known or suspected past hepatitis B infection,
 - blood transfusion(s) prior to 1990,
 - current or prior IV drug users,
 - current or prior dialysis,
 - household contact with hepatitis B infected patient(s),
 - current or prior high-risk sexual activity,
 - body piercing or tattoos,
 - mother known to have hepatitis B
 - history suggestive of hepatitis B infection, e.g., dark urine, jaundice, right upper quadrant pain.
3. Additional patients at the discretion of the investigator

The management guidelines, in Section 6.3.3, are provided according to the results of the baseline assessment of viral load and serological markers for hepatitis B.

Screening for hepatitis C

Patients with any of the following risk factors for hepatitis C should be tested using quantitative RNA-PCR

- known or suspected past hepatitis C infection (including patients with past interferon ‘curative’ treatment),
- blood transfusions prior to 1990,
- current or prior IV drug users,
- current or prior dialysis,

- household contact of hepatitis C infected patient(s),
- current or prior high-risk sexual activity,
- body piercing or tattoos,

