Data will be summarized with respect to demographic and baseline characteristics, efficacy observations and measurements, safety observations and measurements, and pharmacokinetic measurements. Categorical data will be presented as absolute frequencies and percentages. For continuous data, N, mean, standard deviation, median, minimum, and maximum will be presented.

It is planned that the data of each arm will be analyzed independently of the other arm once the number of patients needed for analysis was reached.

For simplification, populations for analysis, and the analysis of patient demographics/other baseline characteristics, treatment, primary and secondary efficacy variables, and safety will

be described without referring to a specific arm. As mentioned above, the methods of analysis will be applied to each arm separately.

In a period of 46 months, so far 8 patients have been enrolled in arm III of this trial. It is deemed very unlikely, that a further extension of the enrollment period will result in the required number of patients in arm III of this trial. Therefore, enrollment in arm III will be stopped. However, patients already enrolled into arm III will continue to be treated and observed as foreseen by the protocol. The final analysis of arm III will be done when all patients have completed the study or discontinued prematurely. Since the sample size required for the decision algorithm will not be reached, data for arm III will be summarized descriptively, and results will be interpreted purely exploratively.

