Clinical Development

RAD001

CRAD001C24114 / NCT00767819

Multicenter, triple-arm, single-stage, phase II trial to determine the preliminary efficacy and safety of RAD001 in patients with histological evidence of progressive or metastatic bone or soft tissue sarcomas

RAP Module 3 – Detailed statistical methodology

Author:

[REDACTED]

Document type: RAP Documentation

Document status: Final 1.0

Release date: 07-Jul-2011

Property of Novartis
Confidential

May not be used, divulged, published or otherwise disclosed
without the consent of Novartis

Novartis approval signatures for:

RAP Module 3 – Detailed statistical methodology

Signature

Date

Signature

Date

1 Data analysis

This was a non-randomized, multicenter, triple-arm, phase II trial evaluating the treatment of RAD001 in the following three arms: in patients with progressive or metastatic bone or soft tissue sarcoma (except for GIST), in patients with progressive or metastatic GIST after failure or intolerance of treatment with imatinib or sunitinib, and in patients with progressive or metastatic alveolar soft part sarcoma (ASPS), respectively.

The study was designed to assess the activity, safety, and tolerability of the therapy with RAD001 in progressive bone or soft tissue sarcoma in the **three** arms each.

The data were analyzed by Novartis. Any data analysis carried out independently by the investigator(s) was recommended to be submitted to Novartis before publication or presentation. It was planned that the data from participating centers in this protocol were combined within each of the arms, so that an adequate number of patients was available for analysis.

Data were summarized with respect to demographic and baseline characteristics, efficacy observations and measurements, safety observations and measurements, and pharmacokinetic measurements. Categorical data were presented as absolute frequencies and percentages. For continuous data, N (the number of valid observations), N miss. (the number of missing observations), mean, standard deviation, median, minimum, and maximum were presented.

It was planned that the data of each arm were to be analyzed and reported independently of the other arm once the number of patients needed for analysis was reached. However, the methods described in this analysis plan apply for all three arms, if not otherwise indicated.

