1.6 Sample size calculation

The study followed an exact binomial single-stage design in each arm. (A'Hern 2001). Values of P_0 and P_1 followed the recommendation of the EORTC Soft Tissue and Bone Sarcoma Group's previous publication evaluating PFS in STS patients treated with 2nd line active and inactive compounds.

In arm I (patients with bone and soft tissue sarcoma except for GIST), the study required 36 evaluable subjects to decide whether the proportion responding (best overall response of CR, PR or SD), p , was less than or equal to $p_0 = 20\%$ or greater than or equal to $p_1 = 40\%$ (Table 10-1). In arm II or III (patients with GIST after failure or intolerance of 1st and 2nd line treatment with imatinib or sunitinib, and patients with progressive or metastatic alveolar soft part sarcoma (ASPS), respectively), the study required 24 evaluable subjects to decide whether the proportion responding best overall response of CR, PR or SD), p , was less than or equal to $p_0 = 20\%$ or greater than or equal to $p_1 = 40\%$.

If the number of responses in arm I was 11 or more, the null hypothesis that p is less than or equal to 20% was to be rejected with a target type I error rate of 10% and an actual error rate of 8.9%. If the number of responses in arm I was 10 or less, the alternative hypothesis that p is greater than or equal to 40% was to be rejected with a target type II error rate of 10% and an actual error rate of 9%.

If the number of responses in arm II or arm III, respectively, was 8 or more, the null hypothesis that p is less than or equal to 20% was to be rejected with a target type I error rate of 10% and an actual error rate of 8.9%. If the number of responses in arm II was 7 or less, the alternative hypothesis that p is greater than or equal to 40% was to be rejected with a target type II error of 20% and an actual error rate of 19.2%.

The designs were estimated with NCSS Trial and PASS 2002.

Table 10-1 Design features for exact binomial single-stage designs

	Arm I	Arm II	Arm III
p_0 (maximum response proportion of an inactive drug)	20%	20%	20%
p_1 (minimum response proportion of an active drug)	40%	40%	40%
Type I error (one-sided test)	10%	10%	10%
Type II error (one-sided test)	10%	20%	20%
Sample size	36	24	24
Accept inactivity at the end if	≤ 10 responders	≤ 7 responders	≤ 7 responders
Reject inactivity at the end if	≥ 11 responders	≥ 8 responders	≥ 8 responders
Actual type I error level	8.9%	8.9%	8.9%

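### SAP 1.4.2 supports rejecting p ≥ 40% from the lower confidence limit, which matches the design at N=36 and N=24 but can exceed the stated type II error at other sizes

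*SAP*

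**What the plan says.** The decision on activity rests on the responder count. SAP 1.4.2: "The absolute number of patients showing a best overall response of CR, PR or SD was determined to conclude preliminary activity or non-activity". SAP 1.6 and its Table 10-1 give the cut-offs. With p0 = 20% and p1 = 40%, inactivity is accepted at 10 or fewer of 36 in arm I and at 7 or fewer of 24 in arms II and III. The stated actual type I error is 8.9% in every arm. The stated actual type II error is 9.0% in arm I (target 10%) and 19.2% in arms II and III (target 20%).

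The interval is Clopper-Pearson, and its level follows from the type I error: "Since the one-sided alpha was set to 10%, two-sided 80% confidence intervals were presented". It is then given a supporting role: "the lower limit of the confidence interval was used to support the decision in favor of p_0 or p_1". The negative half of that reading is "if the lower limit of the confidence interval overlapped p_0 , the hypothesis that p is greater than or equal to p_1 could be rejected". The upper limit is not mentioned.

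On scope, SAP section 1 says "the methods described in this analysis plan apply for all three arms, if not otherwise indicated". Section 10 of the current protocol, however, notes that "so far 8 patients have been enrolled in arm III of this trial", stops enrolment there, and makes the arm III analysis descriptive and exploratory.

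**The concern.** An 80% Clopper-Pearson lower limit at or below 20% is the same event as failing to reject p ≤ 20% at one-sided 10%. It says nothing directly about p ≥ 40%. In the single-stage design, a low count rejects p ≥ 40% only because N and the cut-off were chosen together to hold the type II error. The lower-limit clause carries the type I side to any N but takes no account of the type II side.

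This matters because N is not fixed at 36 and 24. The SAP moves the primary analysis from the per-protocol to the ITT set, and SAP 1.1 defines that set by dosing plus a post-baseline tumour assessment or clinical progression. The design sizes are stated in evaluable subjects, and protocol section 4 transfers five ASPS patients from arm I to arm III. The SAP gives no count cut-offs for any other N. In that case the interval clause is the only part of 1.4.2 that can still be applied mechanically, and it could support a statement against 40% at a higher error than the design allows.

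**Working it through.** **Inputs.** p0 = 0.20, p1 = 0.40, N = 36 and 24, cut-offs and type II targets from SAP 1.6; one-sided 10% and two-sided 80% Clopper-Pearson from SAP 1.4.2. Other N are assumed.

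**1. The plan's own figures.** Type I error = P(X ≥ r | N, 0.20); type II error = P(X ≤ r − 1 | N, 0.40).
- N=36, r=11: 0.0889 and 0.0904.
- N=24, r=8: 0.0892 and 0.1919.

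The stated 8.9%, 9.0% and 19.2% all reproduce.

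**2. Clause against count rule at planned N.** The Clopper-Pearson 80% limits for x of N are the 0.10 quantile of Beta(x, N−x+1) and the 0.90 quantile of Beta(x+1, N−x).
- 10/36: 18.0% to 39.5%. 11/36: 20.4% to 42.4%.
- 6/24: 13.7% to 39.8%. 7/24: 17.0% to 44.2%. 8/24: 20.5% to 48.5%.

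The lower limit crosses 20% exactly at the planned boundaries. In arm I no result with a lower limit at or below 20% has an interval containing 40%. At N=24 only 7/24 does.

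**3. Why 7/24 conflicts.** The two-sided 80% interval leaves 10% in the upper tail, while arm II allows a 20% type II error. The one-sided 80% upper limit at 7/24, the 0.80 quantile of Beta(8, 17), is 39.7%. At the arm's own error level 40% is excluded.

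**4. Other N.** For each N:
- a = largest x with 80% lower limit ≤ 20%. The clause's error is P(X ≤ a | N, 0.40).
- b = largest x whose one-sided upper limit at the arm's type II level (80% in arm II, 90% in arm I) is below 40%. Its error is P(X ≤ b | N, 0.40).
- Counts from b+1 to a reject neither hypothesis.

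| N | target | a | clause error | b | upper-limit error | neither rejected |
|---|---|---|---|---|---|---|
| 20 | 0.20 | 6 | 0.2500 | 5 | 0.1256 | 6 |
| 21 | 0.20 | 7 | 0.3495 | 5 | 0.0957 | 6, 7 |
| 22 | 0.20 | 7 | 0.2898 | 6 | 0.1584 | 7 |
| 23 | 0.20 | 7 | 0.2373 | 6 | 0.1240 | 7 |
| 24 | 0.20 | 7 | 0.1919 | 7 | 0.1919 | none |
| 25 | 0.20 | 8 | 0.2735 | 7 | 0.1536 | 8 |
| 26 | 0.20 | 8 | 0.2255 | 7 | 0.1216 | 8 |
| 33 | 0.10 | 10 | 0.1690 | 9 | 0.0923 | 10 |
| 35 | 0.10 | 10 | 0.1123 | 9 | 0.0575 | 10 |
| 36 | 0.10 | 10 | 0.0904 | 10 | 0.0904 | none |
| 37 | 0.10 | 11 | 0.1333 | 10 | 0.0722 | 11 |

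The clause does not miss its target at every other N: its error is 0.1839 at N=27 and 0.1485 at N=28 (target 0.20), and 0.0882 at N=39 (target 0.10). Whether the target is met depends on N. The upper-limit rule meets it by construction and reproduces both planned boundaries.

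**The case against.** The clause is supportive, not decisive: the count concludes, the interval backs it up, and the verb is permissive. At the planned sizes it changes nothing. The 7/24 case is one outcome in one arm and is coherent with arm II's chosen 20% type II error. All of this stands. A reader might infer that the SAP treats plain non-significance as proof of inactivity. The documents do not support that, because at 36 and 24 the same boundary is a pre-specified decision with a disclosed error for rejecting p ≥ 40%.

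The off-size figures are hypothetical, and protocol 5.2 replaces patients who withdraw early, which limits drift. Nor is the inflation peculiar to the clause. Keeping the count cut-off of 7 unchanged gives the same 35.0%, 29.0% and 23.7% at N = 21, 22 and 23, and 41.6% against the clause's 25.0% at N=20. The shared cause is that no cut-offs exist for other N. That also stands, but it does not rescue the clause. It was offered as support for the decision, and at N = 25 or 26 it would call 8 responders inactive where the unchanged count rule would call them active.

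A reader might also infer that arm III faces a very high false-rejection rate. Applied mechanically, the clause would give 63.3% at N=10 and 59.4% at N=8. Section 10 of the current protocol has withdrawn the decision for that arm, however, and the SAP (July 2011) sizes arm III at 24 and predates the protocol's July 2013 status. The fair criticism is only that the SAP carries no matching exemption.

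**Conclusion.** The clause is wrong as a statement of inference: a lower limit cannot by itself justify rejecting p ≥ 40%. In practice it is harmless at N=36 and N=24, apart from an unexplained mismatch between the conclusion and the printed interval at 7/24. Its real weakness appears only if the ITT set is not of planned size. The error of rejecting p ≥ 40% can then exceed the target, reaching 35.0% against 20% in arm II (N=21) and 16.9% against 10% in arm I (N=33) among the sizes tabulated. This rests on exact binomial calculation at p = 40% and on an assumed range of N, since the documents do not report the achieved ITT sizes. It is worth correcting, but it does not undermine the design.

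**What to change.** Keep the count rule of SAP 1.6 as the sole decision at N=36 (arm I) and N=24 (arm II). Replace the interval clause in SAP 1.4.2 with:

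> p ≤ 20% is rejected if the lower limit of the 80% interval exceeds 20%. If the ITT size is not the planned one, p ≥ 40% is rejected only if the one-sided upper limit at the arm's own type II level (90% for arm I, 80% for arm II) is below 40%. If neither hypothesis is rejected, the result is inconclusive.

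For 7/24, report that p ≥ 40% is rejected at the arm's 20% type II level and that the two-sided 80% interval still includes 40%. Add a sentence aligning the SAP with protocol section 10: no activity or inactivity decision is drawn for arm III. In the same edit, correct the pointer in SAP 1.4.2 to protocol section 10.2, which covers demographics; the cut-offs are in 10.6.

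The cost is a few sentences. Arm I's upper limit is already the upper end of the reported interval, and arm II needs one further quantile. The downside is that some off-size results, such as 7/22 or 10/33, become inconclusive rather than inactive. Nothing changes at the planned sizes.

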5.2 Premature patient withdrawal

Patients must be withdrawn from the study for any of the following reasons:

- Withdrawal of informed consent
- Pregnancy
- Study drug discontinuation
- Progression of tumor
- Unacceptable toxicity
- Patients also should be withdrawn at any time if the investigator concludes that it would be in the patient's best interest for any reason.

The reason for premature patient withdrawal from the study must be recorded on the Study Completion CRF.

Protocol violations should not lead to patient withdrawal unless they indicate a significant risk to the patient's safety.

Patients may voluntarily withdraw from the study for any reason at any time. They may be considered withdrawn if they state an intention to withdraw, or fail to return for visits, or become lost to follow up for any other reason.

For patients who are lost to follow-up (i.e. those patients whose status is unclear because they fail to appear for study visits without stating an intention to withdraw), the investigator should show "due diligence" by documenting in the source documents steps taken to contact the patient, e.g. dates of telephone calls, registered letters, etc.

Patients who are prematurely withdrawn from the core study will be replaced by an equal number of newly enrolled patients.

6 Treatment

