10.2 Patient demographics/other baseline characteristics

Demographic and background information will be summarized for the safety, the ITT, and the PP population, using frequency distributions for categorical variables and descriptive statistics of mean, standard deviation, minimum, median and maximum for continuous variables. Background information includes prior medication, past/current medical conditions, diagnosis and extent of cancer, ECOG performance status and tumor evaluation at baseline.

Medical history will be coded using MedDRA and will be presented by system organ class, MedDRA preferred term and treatment group. Separate tables will be provided for past medical condition and current medical condition. Prior medication will be coded according to WHO Drug Reference List.

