For simplification, populations for analysis, and the analysis of patient demographics/other baseline characteristics, treatment, primary and secondary efficacy variables, and safety were described without referring to a specific arm. As mentioned above, the methods of analysis were applied to each arm separately.

Changes from the analysis pre-planned in the protocol:

1. Although planned in the protocol, the central radiologic review was only incompletely performed due to a variety of reasons (no images submitted from local to central radiologist, when already the first tumor assessment resulted in an overall lesion response of 'progressive disease'; or images were not assessable according to the central radiologist). An incomplete sequence of central assessments cannot be used to derive the primary and secondary efficacy variables. Thus, the trial will be analyzed based on local tumor assessments only.
2. The intention-to-treat (ITT) set will be used for the primary efficacy analysis rather than the per-protocol (PP) set, since this is what is recommended by RECIST criteria (version 1.0, see [Therasse et al. 2000](#): 'All patients included in the study must be assessed for response to treatment, even if there are major protocol treatment deviations or if they are ineligible. [...] All conclusions should be based on all eligible patients.')

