1.1 Populations for analysis

The **safety set** consisted of all patients who received at least one dose of study drug and had at least one post-baseline safety assessment. Patients were analyzed according to treatment received. Of note, the statement that a patient had no adverse events also constituted a safety assessment.

The **intent-to-treat (ITT) set** consisted of all patients who received at least one dose of study drug and had at least one post-baseline assessment of the primary efficacy variable (target/non-target lesion assessment according to RECIST). Patients without any post-baseline assessment of tumor were included if they were defined as progressive disease based on clinical evaluation.

The **per-protocol (PP) set** consisted of all patients of the intent-to-treat population who did not show any major protocol violations. As major protocol violations were considered those that may have an impact on the study outcome. Criteria that were assumed to have such an impact were defined in a Review Meeting before database lock.

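### SAP 1.4.2 accepts a response rate of at least 40% on evidence that only rules out 20% or less, and the fixed cut-offs of 11 and 8 hold their stated error rates only at N = 36 and N = 24

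*SAP*

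**What the plan says.** Protocol 10.6 and SAP 1.6 describe an exact binomial single-stage design with p0 = 20% and p1 = 40%. Arm I needs 36 evaluable patients and arms II and III need 24 each. SAP 1.6 puts the positive outcome this way: "If the number of responses in arm I was 11 or more, the null hypothesis that p is less than or equal to 20" per cent is to be rejected. The cut-off in arms II and III is 8.

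SAP 1.4.2 adds a second rule based on the two-sided 80% Clopper-Pearson interval. If the lower limit overlaps p0, p ≥ p1 could be rejected. The sentence continues: "on the other side, if the lower limit of the confidence interval excluded p_0", then "the hypothesis that p is greater than or equal to p_1 could be accepted".

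Three other provisions determine the N to which the counts are applied:
- SAP section 1, list of changes, item 2: "The intention-to-treat (ITT) set will be used for the primary efficacy analysis rather than the per-protocol (PP) set".
- SAP 1.1 defines the ITT set as treated patients with a post-baseline tumour assessment, and adds: "Patients without any post-baseline assessment of tumor were included if they were defined as progressive disease based on clinical evaluation".
- Protocol 5.2: "Patients who are prematurely withdrawn from the core study will be replaced by an equal number of newly enrolled patients".

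For arm III, protocol section 10 says: "Since the sample size required for the decision algorithm will not be reached, data for arm III will be summarized descriptively".

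**The concern.** The two parts of the SAP draw different conclusions from the same data. In 1.6, reaching the cut-off rejects p ≤ 20%. In 1.4.2, the same result is turned into acceptance of p ≥ 40%. Only the first follows. The report could therefore say that the rate set for an active drug has been accepted when the observed rate is about 31% or 33%, on the trial's primary endpoint.

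The second issue depends on N. The counts were derived for exactly 36 and 24 patients. Under protocol 5.2 a withdrawn patient is replaced. If that patient had a post-baseline tumour assessment or clinical progression, SAP 1.1 keeps the patient in the ITT set as well, so the set can grow beyond plan. The interval limit adapts to the N analysed and the fixed count does not. Apart from describing the interval as support, neither document says what to do if the two disagree.

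**Working it through.** **Inputs.** p0 = 20%, p1 = 40%, one-sided alpha 10%, N = 36 with cut-off 11 and N = 24 with cut-off 8 (protocol 10.6, SAP 1.6); exact two-sided 80% Clopper-Pearson interval on the ITT set (SAP 1.4.2).

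**Formulas.** For cut-off r and sample size N:
- type I error = P(X ≥ r | N, 0.20)
- type II error = P(X ≤ r − 1 | N, 0.40)
- lower limit L solves P(X ≥ x | N, L) = 0.10; upper limit U solves P(X ≤ x | N, U) = 0.10

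**Step 1: the plan's own figures.** For 36 and 11 the type I error is 0.0889 and the type II error 0.0904. For 24 and 8 they are 0.0892 and 0.1919. These match the stated 8.9%/9.0% and 8.9%/19.2%, so the sample-size arithmetic is right.

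**Step 2: what the interval rule tests.** By the definition of L, L > 20% holds exactly when P(X ≥ x | N, 0.20) < 0.10. That is the one-sided test of p ≤ 20%, and p1 does not enter it.

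| Responders | Estimate | 80% CI | SAP 1.4.2 reading |
|---|---|---|---|
| 10/36 | 27.8% | 18.0–39.5% | reject p ≥ 40% |
| 11/36 | 30.6% | 20.4–42.4% | accept p ≥ 40% |
| 14/36 | 38.9% | 27.8–50.9% | accept p ≥ 40% |
| 7/24 | 29.2% | 17.0–44.2% | reject p ≥ 40% |
| 8/24 | 33.3% | 20.5–48.4% | accept p ≥ 40% |
| 9/24 | 37.5% | 24.1–52.6% | accept p ≥ 40% |

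Every count from 11 to 14 of 36, and 8 or 9 of 24, accepts 40% with an estimate below 40%. The lower limit first passes 40% at 19/36 (52.8%, L = 40.9%; 18/36 gives 38.2%) and at 14/24 (58.3%, L = 43.3%; 13/24 gives 39.2%).

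The chance of accepting p ≥ 40% when it is false is P(X ≥ r | N, p). For p = 25%, 30% and 35% it is 27%, 53% and 77% at N = 36, and 23%, 44% and 64% at N = 24.

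**Step 3: fixed cut-offs at other N.** All N other than 36 and 24 are assumptions.

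| Cut-off | N | Type I | Type II | L at the cut-off |
|---|---|---|---|---|
| 11 | 35 | 7.5% | 11.2% | 21.0% |
| 11 | 36 | 8.9% | 9.0% | 20.4% |
| 11 | 37 | 10.5% | 7.2% | 19.8% |
| 11 | 38 | 12.2% | 5.7% | 19.3% |
| 11 | 40 | 16.1% | 3.5% | 18.3% |
| 8 | 23 | 7.2% | 23.7% | 21.4% |
| 8 | 24 | 8.9% | 19.2% | 20.5% |
| 8 | 25 | 10.9% | 15.4% | 19.6% |
| 8 | 26 | 13.1% | 12.2% | 18.8% |
| 8 | 28 | 18.2% | 7.4% | 17.4% |

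Both targets are met only at the design N. Above it, 11 responders (N = 37–40) or 8 responders (N = 25–28) are active by count, while the interval rule rejects p ≥ 40%. At 11/40 the whole interval (18.3–38.5%) lies below 40%. If p = 20%, that one conflicting count has probability P(X = 11), from 5.3% (N = 37) to 7.3% (N = 40), in arm I, and P(X = 8), from 6.2% (N = 25) to 9.2% (N = 28), in arm II.

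**Step 4: cut-off at the actual N.** The smallest r with P(X ≥ r | N, 0.20) ≤ 0.10 equals the smallest r with L > 20% at every N from 20 to 49. One exact test therefore removes the conflict.

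**The case against.** The interval is described only as support, and the text says could be accepted. In a two-point design, accept and reject are customary shorthand for active and inactive, and Table 10-1 uses the same idiom. SAP 1.6 already states the inference correctly, and at the planned N both rules give the same call. All of that is true, and it limits the consequence of the first part to the claim made. It does not make the sentence in 1.4.2 valid.

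On the second part, the final N is unknown and could fall below plan: protocol section 4 moves five ASPS patients from arm I to arm III, and ITT drops patients with neither a tumour assessment nor clinical progression. Below plan the fixed counts keep type I error under 10% and lose power. Replacement might also be meant only to restore the evaluable number. These points stand, and they are why this part is conditional.

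The exact cut-off has a real price. At N = 37, moving from 11 to 12 takes type I error from 10.5% to 5.2% and type II error from 7.2% to 13.3%. At N = 25, moving from 8 to 9 takes them from 10.9% to 4.7% and from 15.4% to 27.4%. One could reasonably tolerate a small excess in a preliminary screen. But the plan sets a 10% one-sided alpha and supplies an interval rule that enforces it, so departing from it should be a stated choice.

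**Conclusion.** The concern holds. The acceptance of p ≥ 40% in SAP 1.4.2 is an error of inference at the planned N and needs no assumption: 11/36 and 8/24 trigger it, against the 19/36 and 14/24 needed for a lower limit above 40%. It affects what is claimed and leaves the go/no-go decision at N = 36 and N = 24 unchanged.

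The cut-off problem is conditional on an ITT N above 36 or 24, which protocol 5.2 and the ITT definition allow but the documents do not confirm. One patient over plan is enough to exceed the 10% alpha and to put the two rules in conflict at a particular count. Arm III is unaffected, because the current protocol makes it descriptive. This should be fixed, because it concerns the wording and the rule of the primary conclusion.

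**What to change.** 1. In SAP 1.4.2, replace the acceptance of p ≥ p1 with a statement that p ≤ p0 is rejected at one-sided 10% and the rate is concluded to exceed 20%. Report the estimate and the 80% interval, and do not claim that 40% is established.
2. For arms I and II, base the decision on the one-sided 10% exact binomial test at the actual ITT N:
   - Arm I: 10 responders for N = 29–32, 11 for 33–36, 12 for 37–40, 13 for 41–45.
   - Arm II: 8 for N = 21–24, 9 for 25–28, 10 for 29–32.
3. Keep the inactivity side as designed, with type II targets of 10% (arm I) and 20% (arm II). Do not require the upper limit to fall below 40%: 7/24, an inactive result by design, has an upper limit of 44.2%. Report the attained type I and type II errors at the actual N, and say where the type II target is missed.
4. State in the SAP that no decision rule applies to arm III.
5. Correct the cross-reference. SAP 1.4.2 and protocol 10.4.2 point to section 10.2 for the rules, but that section is headed "10.2 Patient demographics/other baseline characteristics". The rules are in protocol 10.6.

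The cost is a few sentences and a short table. The claim becomes more modest when the cut-off is only just met. Just above plan, power falls: type II error is 13.3% at N = 37 and 10.9% at N = 38 with cut-off 12, and 27.4% at N = 25 and 22.6% at N = 26 with cut-off 9.
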